6.2 PREPARATION/HANDLING/STORAGE/ACCOUNTABILITY

Study drug packaging will be overseen by the Sponsor's clinical trial supplies department and bear a label with the identification required by local law, the protocol number, drug identification and dosage.

The packaging and labeling of the study medication will be in accordance with the Sponsor's standard and local regulations.

The investigational site will acknowledge receipt of IMPs and confirm the shipment condition and content. Any damaged shipments will be replaced.

Upon arrival of the IMPs at the site, site personnel will complete the following:

- Check the IMPs for damage.
- Verify proper identity, quantity, integrity of seals and temperature conditions.
- Report any deviations or product complaints to the Monitor upon discovery.

The qualified individual responsible for dispensing the study treatment will prepare the correct dose according to the defined dose-level.

The Investigator or delegate must confirm appropriate temperature conditions have been maintained during transit for all study treatment received and any discrepancies are reported and resolved before use of the study treatment.

Only participants enrolled in the study may receive study treatment and only authorized site staff may supply or administer study treatment. All study treatments must be stored in a secure, environmentally controlled, and monitored (manual or automated) area in accordance with the labeled storage conditions with access limited to the Investigator and authorized site staff.

The Investigator is responsible for study treatment accountability, reconciliation, and record maintenance (i.e., receipt, reconciliation and final disposition records).

IMPs will either be disposed of at the study site according to the study site's institutional standard operating procedure (SOP) or returned to the Sponsor with the appropriate documentation. The site's method of IMP destruction must be agreed upon by the Sponsor. Local or institutional regulations may require immediate destruction of used IMP for safety reasons. The site must obtain written authorization from the Sponsor before any IMP is destroyed, and IMP destruction must be documented on the appropriate form.

Further guidance and information for the final disposition of unused study treatment are provided in the Pharmacy Manual.

6.3 MEASURES TO MINIMIZE BIAS: RANDOMIZATION AND BLINDING

6.3.1 Method of Treatment Assignment

This is an open-label, non-randomized study. Participants who fulfill all of the inclusion criteria and none of the exclusion criteria are eligible to participate in the study and will be assigned to a treatment group/dose in consultation with the Sponsor. For Part I and Part II of the study, the assigned dose will be documented in the Confirmation of Enrollment and a participant number will be assigned. A participant Enrollment and Identification Code List must also be maintained by the Investigator.

6.4 TREATMENT COMPLIANCE

The qualified individual responsible for dispensing the study treatment will prepare the correct dose according to the defined dose-level and the instructions given in the Pharmacy Manual. This individual will write the date dispensed and participant number on the study treatment box label and on the Drug Accountability Record. This individual will also record the study treatment number received by each participant during the study.

6.5 CONCOMITANT THERAPY

6.5.1 Permitted Therapy

Any medication or vaccine (including over-the-counter [OTC] or prescription medicines, approved dietary and herbal supplements, nutritional supplements) used by a participant during screening until the follow-up visit must be recorded along with reason for use, dates of administration (including start and end dates) and dosage information (including dose and frequency). The Medical Monitor should be contacted if there are any questions regarding concomitant or prior therapy.

All concomitant medications should be reported to the Investigator and recorded on the Concomitant Medications eCRF. All therapy and/or medication administered to manage adverse events should be recorded on the AE eCRF.

6.5.1.1 Radiotherapy

The use of palliative radiotherapy is allowed at any time during the study, **except for:**

- On days when RO7172508 is administered.
- During DLT evaluation period.
 - If radiotherapy is administered during the DLT evaluation period, the participant will not be evaluable.

Participants should not receive study treatment during radiation treatment.

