The use of palliative radiotherapy is allowed at any time during the study, **except for:**

- Days where study drug is administered.
- During the DLT evaluation window.
 - If radiotherapy is administered during the DLT evaluation window, the participant will not be evaluable.

Participants should not receive study treatment during radiation treatment.

Prohibited Therapy

[figure not shown]
The use of the following therapies is prohibited during the study and for at least 28 days prior to initiation of study treatment (unless otherwise specified):

- Investigational or unlicensed/unapproved agents
- Immunotherapy/radio-immunotherapy
- Chemotherapy/targeted therapy
- Radiotherapy (with the exception of limited-field palliative radiotherapy).
- Biologic agents (e.g., bevacizumab)
- Chronic use of steroids (inhaled and topical steroids are permitted).
- Administration of a live, attenuated vaccine within 28 days before Cycle 1 Day 1 or anticipation that such a live attenuated vaccine will be required during the study.

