The Part II dose-escalation will start with a dose of 1.6 mg (flat dose) IV Q3W (Section 4.3 Dose Justification) if this dose has been reached in Part I and considered safe. In the eventuality that Part I has been stopped because of the occurrence of a RO7172508-related Grade ≥ 2 AE (or DLT) then, the starting-dose of Part II will not exceed the dose-level at which the AE that delineated the end of Part I occurred. Furthermore, the grade and type of AE will also be considered, when choosing the dose-level for Part II. In the eventuality that the Sponsor decides to initiate Part II in the absence of an observed RO7172508-related Grade ≥ 2 toxicity and prior to the dose-level reaching 1.6 mg, then the starting-dose of Part II will not exceed the highest dose tested in Part I. If the starting-dose of Part II is the same as the last dose in Part I, the participant treated at the last dose in Part I could be considered as the first participant of the cohort for Part II. If the initial dose is not tolerated, then participants for the subsequent cohort may be enrolled at a lower RO7172508 dose than the initially selected Part II starting-dose. The maximum dose of RO7172508 will be 400 mg (flat dose IV). The initial dosing regimen in Part II may also be adapted depending on emerging data in Part I.

In Part II dose-escalation, a minimum of 3 participants per cohort *will be enrolled who have a baseline sCEA level ≤ 20 ng/ml*. Participants within a cohort will be treated in a sequential manner with one week between the first and second participant, and at least one day between subsequent participants. However, if the first participant experiences a DLT within the first 7 days, then the time between the treatment of subsequent participants within the same cohort may be increased. The DLT evaluation window in Part II is defined as a period of 3 weeks after the first administration of RO7172508 in an IV Q3W schedule. Based on emerging data, the interval between dosing of each participant within a cohort or the DLT window may be adjusted if deemed appropriate by the Investigators and/or the Sponsor.

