For each cohort, all participants will be followed through a 3-week DLT window (i.e., 21 days *after the first dose of RO7172508*). If fractionated dosing is implemented in Cycle 1 to improve tolerability, the DLT window will be extended to include the cycle where the planned target dose is administered in full i.e., *Cycle 1 Day 1 until the end of Cycle 2*. The DLT window will therefore be 6 weeks (42 days), or 8 weeks (56 days) if treatment has been delayed for no more than 14 days.

A new cohort can be opened when at least 3 evaluable participants of the previous cohort have completed the DLT window. *At least 3 evaluable participants must have a baseline sCEA level of ≤ 20 ng/ml.* If participants experience a DLT before completion of the last day of their DLT window, they will be considered as having completed their DLT window. Prior to opening a new cohort, the logistic regression model will be updated with the treatment outcome (i.e., the occurrence of DLT) and a new estimate of the MTD will be derived.

Enrollment into the next cohort will only resume after the Sponsor and the Investigators have jointly decided on the next dose-escalation step. Subject to clinical judgment, a new cohort of participants will be dosed at the new estimate of the MTD or the highest allowable dose based on pre-specified safety constraints as described below, whichever is lower and as guided by the mCRM-EWOC model. The design will continue as described, assigning participants to the MTD as estimated from all of the DLT data cumulatively, until one of the pre-defined stopping criteria is satisfied (see Section 4.1.4) or the pre-determined sample size of 60 DLT-evaluable participants is reached, whichever comes first. *Depending on emerging PK and safety data, the dose escalation may be evaluated taking into account sCEA levels at baseline in a sensitivity analysis (i.e. dose escalating more conservatively in the event toxicity is associated with low baseline sCEA levels).*

Built-in safety constraints are in place to prevent exposing participants to undue risk of toxicity, i.e., for Q3W dosing schedule, maximum allowable dose-increment, in absence of DLT, will be a maximum of 100%; if one DLT occurs then, an increment of 50% maximum will be allowed. The maximum dose that could be assessed in Part II will be 400 mg IV (see Section 4.3).

Provisional dose-levels in absence of DLT are listed in [Table 9](#).

Table 9 Provisional Dose Levels in Absence of DLT

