4.1.3.1 Dose-Limiting Toxicities

For the purpose of this study, a DLT will be defined as *any of the following events occurring during the DLT window and not attributable to underlying disease or intercurrent illness*:

- Hematological toxicities defined as:
 - Grade 4 neutropenia (i.e., absolute neutrophil count [ANC] < 0.5×10^9 cells/L for a minimal duration of one week).
 - Grade 3 and 4 febrile neutropenia.
 - Grade 4 thrombocytopenia lasting > 48 hours
 - Grade 3 thrombocytopenia associated with bleeding episodes.

- Grade ≥ 3 non-hematological toxicity with the following exceptions:
 - Alopecia (any grade)
 - Grade 3 nausea or vomiting that resolves to Grade ≤ 1 with or without supportive therapy within one week.
 - Grade 3 hypophosphatemia and transient Grade 3 hyperbilirubinemia resolved within one week.
 - Grade ≥ 3 fatigue that resolves to Grade ≤ 2 within one week.
 - Fever $> 40^{\circ}\text{C}$ (i.e., Grade 3) that occurs within 48 hours of RO7172508 infusion and improves to $\leq 40^{\circ}\text{C}$ (Grade ≤ 2) within 48 hours and fully resolves within one week.
 - Grade 3 arthralgia that can be adequately managed with supportive care or that improves/resolves to Grade ≤ 2 within one week.
 - Grade 3 diarrhea, colitis, enteritis that resolves to Grade ≤ 1 within one week with no fever or dehydration.
 - Laboratory values of Grade ≥ 3 that are judged not clinically significant by the Investigator.
 - Grade 3 tumor pain that starts within 24 hours of infusion and improves/resolves to Grade ≤ 2 within one week.
 - Grade 3 hypoxia that starts within 24 hours of infusion and improves/resolves to Grade ≤ 2 within one week.
 - In participants with lung lesions, Grade 3 transient dyspnea secondary to localized lung edema that starts within 24 hours of infusion and resolves to Grade 1 or baseline within one week, and transient bronchospasm that resolves within 24 hours.
 - In participants with liver lesions, Grade 3 transient increase of bilirubin, transaminases (aspartate aminotransferase [AST]/alanine aminotransferase [ALT]) and/or gamma-glutamyl transferase (GGT) that starts within 24 hours of infusion and recovers to Grade 1 or baseline within one week.

Failure to recover from any RO7172508-related toxicity that results in a dose-delay of more than 14 days (any regimen) is defined as a DLT.

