9.3 POPULATIONS FOR ANALYSES

For purposes of analysis, the following populations are defined in [Table 21](#).

Table 21 Analysis Populations

Population	Description
Efficacy	All participants who received at least one dose of RO7172508.
Safety	All participants enrolled in the study who received at least one dose of study treatment (RO7172508 and/or obinutuzumab if applicable) will be included in the safety population. Unless otherwise specified, the safety population will be the default analysis set used for all analyses.
DLT evaluable	DLT-evaluable participants are those who have completed the DLT window without a DLT, or participants who reported with a DLT. This population will be used in the determination of the MTD.
Pharmacokinetic	All participants who have received at least one dose of study treatment and who have data from at least one post-dose sample will be included in the PK analysis population. Participants will be excluded from the PK analysis population if they significantly violate the inclusion or exclusion criteria, deviate significantly from the protocol, or if data are unavailable or incomplete which may influence the PK analysis. Excluded cases will be documented together with the reason for exclusion. All decisions on exclusions from the analysis will be made prior to database closure.
Immunogenicity	Participants who had at least one pre-dose and one post-dose ADA assessment will be included and analyzed according to the treatment they actually received. The relationship between ADA status and safety, efficacy, PK, and biomarker endpoints will be analyzed and reported descriptively via subgroup analyses.

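### The palliative-radiotherapy rule has no exception for a DLT that came first, so it conflicts with Table 21 on who counts towards the MTD

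*Combined protocol and SAP*

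**What the plan says.** - **Section 6.5.1.1** does not allow palliative radiotherapy in the DLT period, and adds: "If radiotherapy is administered during the DLT evaluation period, the participant will not be evaluable". The **synopsis (1.1)** carries the same rule: "If radiotherapy is administered during the DLT evaluation window, the participant will not be evaluable". Neither depends on whether a DLT came first.
- **Section 9.3, Table 21**: "DLT-evaluable participants are those who have completed the DLT window without a DLT, or participants who reported with a DLT". It contains no radiotherapy exclusion, and it continues: "This population will be used in the determination of the MTD".
- **Section 4.1.2.2** on an early DLT: "If participants experience a DLT before completion of the last day of their DLT window, they will be considered as having completed their DLT window".
- **Section 4.1.2.2** on the length of the window: "The DLT evaluation window in Part II is defined as a period of 3 weeks after the first administration of RO7172508 in an IV Q3W". With fractionated dosing it becomes 42 days, or 56 if treatment is delayed.
- **Section 7.1** permits replacement when the DLT period is not completed for reasons unrelated to the drug. It does not mention a participant who has a DLT and is then irradiated.

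**The concern.** Take a participant with a DLT on Day 5 and palliative radiotherapy on Day 15. Under Section 6.5.1.1 that person is not evaluable; under Table 21 the same person is. No section ranks one rule above the other.

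The DLT-evaluable set feeds the dose-toxicity model and the count of 3 evaluable participants needed to open the next cohort. The increment cap depends on whether a DLT has been counted. If the radiotherapy rule is followed to the letter, a primary-endpoint event that was actually observed leaves these inputs. If a DLT-free participant then fills the place, the cohort looks cleaner than it was.

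**Working it through.** **1. The passages side by side**

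| Participant | 6.5.1.1 and synopsis | Table 21 |
|---|---|---|
| DLT, then radiotherapy in the window | not evaluable | evaluable |
| Radiotherapy in the window, then DLT | not evaluable | evaluable |
| Radiotherapy in the window, completed without DLT | not evaluable | evaluable |

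The first row is the one that matters most. The other two show that Table 21 also needs an edit.

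**2. Inputs for the size of the effect** (Appendix 8, Section 1)

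- Model: logit p(d) = α + β·ln(d/100).
- Prior: mixture of 10% informative and 90% minimally informative components with the printed means and covariances. The same sentence also prints a weight of 0.25.
- Next dose: the grid dose with the highest P(0.20 ≤ p ≤ 0.35), subject to P(p > 0.35) < 0.25 and the increment cap.
- Cap: 100% before any DLT, 50% from the first DLT. The maximum dose is 400 mg.
- Earlier cohorts: 3 participants each, no DLTs, as in the mock runs.

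**3. Reproducing the plan's figures**

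A refit by importance sampling on the stated dose grid returns all nine 0-DLT rows and all nine 1-DLT rows of Appendix 8 Table 1 (one differs by a grid step, 9.6 against 9.5 mg). Using 0.25 as the prior weight gives the same rows.

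In these rows the recommendation is the highest grid dose under the cap. After 40 mg: 40 × 2 = 80 mg with no DLT, 40 × 1.5 = 60 mg with one. After 150 mg: 150 × 2 = 300 mg, against 150 × 1.5 = 225, which falls to 200 mg on the grid.

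**4. One DLT kept against one DLT lost**

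Kept means 1 DLT in 4 participants. Lost means that participant is removed and a DLT-free one completes the cohort (0 in 3). The last column is P(p > 0.35) at the lost-DLT dose, computed on the full 1-in-4 data.

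| Current dose, mg | Next dose, DLT kept | Next dose, DLT lost | Overdose probability on full data |
|---|---|---|---|
| 1.6 | 2.4 | 3.2 | 0.15 |
| 3.2 | 4.8 | 6.4 | 0.12 |
| 6.4 | 9.6 | 12 | 0.10 |
| 12 | 18 | 20 | 0.09 |
| 20 | 30 | 40 | 0.11 |
| 40 | 60 | 80 | 0.15 |
| 80 | 120 | 150 | 0.17 |
| 150 | 200 | 300 | 0.23 |
| 300 | 400 | 400 | 0.17 |

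Counting the kept case as 1 in 3 gives the same next doses. The next dose rises at 8 of 9 levels; at 300 mg the 400 mg ceiling binds either way. At 80 mg after the 40 mg cohort, the model would report an overdose probability of 0.05 on the reduced data against 0.15 on the full data.

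**5. A rarer case, for scale**

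If 2 of 4 participants have DLTs and one is lost, the chosen dose has an overdose probability above 0.25 on the full data at 5 of 9 levels: 0.39 after 1.6 mg, 0.28 after 3.2, 0.29 after 80, 0.28 after 150 and 0.35 after 300. This is less secure, because the refit does not match the printed 2-DLT rows at 6.4 mg (7.9 against 6.4) and 12 mg (15 against 12). The point does not rest on it.

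**The case against.** **Section 4.1.2.2 already resolves it.** A participant with an early DLT is treated as having finished the window, so later radiotherapy would fall outside it and Section 6.5.1.1 would not apply. This is a fair reading and may be what was intended. But the same section defines the window as a fixed period from first dose, and 6.5.1.1 does not refer to the early-DLT sentence. The reading is inferred. For the same reason, Section 4.1.2.2 should not be cited as a flat contradiction of 6.5.1.1; the direct conflict is with Table 21.

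**It should be uncommon, and there are other safeguards.** This stands. Radiotherapy in the window is itself disallowed, and no frequency is given. The event remains an adverse event in the safety population. Dose decisions are joint, use all safety data and can override the model.

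A reader might infer more than the documents support:

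- *The loss is selective, because persistent tumor pain is both a DLT and a reason for radiotherapy.* Section 4.1.3.1 exempts "Grade 3 tumor pain that starts within 24 hours of infusion and improves/resolves to" Grade 2 or below within a week, but it also requires that a DLT not be attributable to underlying disease, so persistent pain is not automatically a DLT. No section links such pain to radiotherapy in this trial.
- *The error always favors a higher MTD.* That is true of a dropped DLT. The same rule also removes irradiated participants without a DLT, which raises the estimated rate.
- *The next cohort would be overdosed.* With one lost DLT, the overdose probability stays under the plan's 0.25 limit at every level.
- *The cap always doubles.* It moves from 50% to 100% only if the lost event is the first DLT in the trial; after any earlier DLT it is already 50%.

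**Conclusion.** The conflict between Section 6.5.1.1 (with the synopsis) and Table 21 is real and stated in plain terms. For a participant with a DLT who is later irradiated in the window, one rule deletes the event from the MTD data and the other keeps it.

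The practical size is modest. The higher next dose at 8 of 9 levels rests on four assumptions: the literal reading of 6.5.1.1 is applied, the lost event is the trial's first DLT, a DLT-free participant takes the place (Section 7.1 does not settle this), and earlier cohorts had 3 participants without DLTs. Under these, the overdose probability on the full data is 0.09 to 0.23.

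It still merits correction. It concerns an observed primary-endpoint event in a first-in-human escalation, and clinical judgment should not have to repair an evaluability rule. Excluding a participant irradiated before any DLT is coherent; the defect is the missing exception.

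**What to change.** Reconcile the evaluability wording in three places:

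- **Section 6.5.1.1 and the synopsis:** state that radiotherapy in the DLT window makes a participant non-evaluable only if no DLT occurred before it. Add that a participant whose DLT came before radiotherapy remains DLT-evaluable and is not replaced.
- **Table 21:** add the matching exclusion for participants irradiated in the window before any DLT. This also settles the other two rows of the comparison: a DLT only after radiotherapy, and completion without a DLT.

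The cost is one sentence in each place. No participants, procedures or recalculation are needed. The change concerns the analysis population only and alters nothing about when radiotherapy is given.

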6.5.2 Prohibited Therapy

All medications (prescription and OTC) taken within 30 days of study screening will be recorded on the appropriate eCRF. As a general rule, no concomitant medication will be permitted, with the exception of medications to treat AEs, unless the rationale for exception is discussed and clearly documented between the Investigator and the Sponsor.

The use of the following therapies is prohibited for at least 28 days prior to initiation of study treatment and during the study, unless otherwise specified below:

- Investigational or unlicensed/unapproved agents
- Immunotherapy/radio-immunotherapy
- Chemotherapy/targeted therapy
- Radiotherapy (with the exception of limited-field palliative radiotherapy; see Section 6.5.1.1).
- Biologic agents (e.g., bevacizumab, erlotinib).
- Chronic use of steroids (inhaled and topical steroids are permitted).
- Administration of a live, attenuated vaccine within 28 days before Cycle 1 Day 1 or anticipation that such a live attenuated vaccine will be required during the study.

6.6 DOSAGE MODIFICATION

In the event a dose-reduction is necessary, any subsequent study treatment will be administered after agreement with the Sponsor.

Should a participant experience a DLT in the first or in subsequent cycles or experience a toxicity of the same nature at the same or higher grade following re-exposure to RO7172508, the Investigator, after discussion with the Sponsor, will have the option to reduce the dose of RO7172508, if deemed clinically beneficial.

A delay of RO7172508 administration for up to two cycles independent of the schedule, will be acceptable to allow for resolution of toxicity to NCI CTCAE Grade ≤ 2 for hematological toxicities or Grade ≤ 1 for non-hematological toxicities (with the exception of a toxicity considered as non-RO7172508-related).

If the toxicity does not resolve to NCI CTCAE Grade ≤ 2 for hematological toxicities or ≤ 1 for non-hematological toxicities and the participant is unable to resume treatment with RO7172508 after this time (omission of two doses), no additional doses will be administered and the participant will be withdrawn from study treatment, unless the participant exhibits a clinical benefit and this is agreed by the Investigator and the Medical Monitor. It should be noted that infusions/cycles not occurring at the anticipated schedule, are considered as delayed, not missed.

Further dose-reductions may be implemented once safety and toxicity data from the dose-escalation have been evaluated.

If a participant experiences obinutuzumab-related toxicity on Day -7 that requires the subsequent administration of obinutuzumab on Day -6 to be delayed, administration of obinutuzumab up to Day -5 is acceptable. Any obinutuzumab-related toxicity should resolve to NCI CTCAE Grade ≤ 2 for hematological toxicities or ≤ 1 for non-hematological toxicities before RO7172508 administration. The first RO7172508 administration can be delayed for up to 1 week and if toxicity persists, the start of RO7172508 treatment will need to be agreed with the Medical Monitor.

